18- For Responders (R) the EoS visit must be completed 16 weeks after last treatment, which is at the latest at Week 28 (V10). Responders (R) may complete EOS at any point after V7 (Week 16) if the patient drops to an EASI 50 score prior to the planned EOS. For Non Responder (NR) patients who have achieved EASI 50 and plan to participate in the extension trial, the EoS visit will be completed no earlier than Week 32. Non Responder patients not participating in the extension trial will complete a V11/FU1 visit between Week 32-44. If a patient should discontinue treatment prematurely every effort should be made to keep the patient in the trial and complete all of the remaining study visits or at a minimum an early EoS visit 16 weeks after last treatment.

[figure not shown]
19- At V1 (Screening) BSA will be assessed for eligibility. From V2 (baseline) onward BSA will be completed as part of SCORAD assessment.

20- Only Non-Responders not participating in the open label extension trial must complete an End of Study Safety Phone Call. V11 and End of Study Safety Phone call can occur on the same day only if the Residual Effect Period (16 weeks after last trial drug infusion) has been reached (WK44). The phone call cannot be performed before the V11.

21- Patients will be asked about their pregnancy status at the End of Study Safety Phone Call.

22- For Non-Responders participating in the open label extension trial, End of Study completion IRT call is registered at V11 as the End of Study Safety Phone Call is not required. For Non-Responders not participating in the open label extension trial, End of Study completion IRT call is registered only at End of Study Safety Phone Call (WK44). V11 is not registered in IRT.

TABLE OF CONTENTS

TITLE PAGE	1
CLINICAL TRIAL PROTOCOL SYNOPSIS	2
FLOW CHART	6
TABLE OF CONTENTS	10
ABBREVIATIONS	13
1. INTRODUCTION.....	16
1.1 MEDICAL BACKGROUND	16
1.2 DRUG PROFILE	17
1.2.1 Mode of Action	17
1.2.2 Nonclinical pharmacology.....	17
1.2.3 Clinical experience	18
1.3 RATIONALE FOR PERFORMING THE TRIAL	20
1.4 BENEFIT - RISK ASSESSMENT.....	20
2. TRIAL OBJECTIVES AND ENDPOINTS.....	22
2.1 MAIN OBJECTIVES, PRIMARY AND SECONDARY ENDPOINTS.....	22
2.1.1 Main objectives.....	22
2.1.2 Primary endpoint	22
2.1.3 Secondary endpoint(s)	22
	
3. DESCRIPTION OF DESIGN AND TRIAL POPULATION	24
3.1 OVERALL TRIAL DESIGN AND PLAN	24
3.2 DISCUSSION OF TRIAL DESIGN, INCLUDING THE CHOICE OF CONTROL GROUP(S)	25
3.3 SELECTION OF TRIAL POPULATION	25

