V1	Screening	- 28 to -7	n/a			$-\infty$	0
V2	Day 1	Day 1	n/a	1 ^A	1	1 ^A	1
V3	Week 2	Day 15	+/- 3	12	18	2	21
V4	Week 4	Day 29	+/- 3	26	32	22	42
V5	Week 8	Day 57	+/- 3	54	60	43	70
V6	Week 12	Day 85	+/- 3	82	88	71	98
V7	Week 16	Day 113	+/- 3	110	116	99	Week 16 visit date

Days are counted relative to the day of first treatment, which is defined as Day 1.

^A Note that measurements made at Day 1 and assigned to the on-treatment period (because mistakenly made after start of infusion of trial treatment) via assessment on date and time (i.e. safety laboratory) will not be assigned to Day 1. Such data will be listed only.

[Table 6.7:1](#) needs to be taken only when the measurement occurs between randomisation date and primary endpoint visit date (Week 16 visit date). Any unscheduled visits after Week 16 visit date will not be taken into account in [Table 6.7:1](#).

For measurements after the primary endpoint visit date (Week 16 visit date), including unscheduled visits, refer to the [Table 6.7:2](#).

Table 6.7: 2 Time windows for assignment of efficacy, safety lab, vital signs, and biomarker measurements to visits for statistical analysis after Week 16 visit date

Visit number/ name	Visit label	Planned day	Time window (Days)				
			Window (per CTP)	Start (per CTP)	End (per CTP)	Start (extended)	End (extended)
V7.1*	Week 16OL					Week 16 visit date+1	126
V8	Week 20	Day 141	+/- 3	138	144	127	154
V9	Week 24	Day 169	+/- 3	166	172	155	182
V10**	EoS for R	Day 197	+/- 3	194	200	183	210/
						LD+16 weeks/EoS visit date	
V11a***	EoS for NR	Day 228	+/- 3	225	231	211	238/
						LD+16 weeks /EoS visit date	
V11b***	EoS for NR	Day 309	+/- 3	306	312	239	LD+16 weeks /EoS visit date

Days are counted relative to the day of first treatment, which is defined as Day 1.

LD = Last dose of treatment

EoS = End of Study

R = Responder

NR = Non-Responder

* For vital signs, measurements after EASI responder-non-responder assessment are assigned to Week 16 (V7), after first open-label (OL) treatment

** V10 EoS applies to patients who responded at Week 16 (up to LD+16 weeks); Non-responders receive the last dose of the BI655130 at that Week 28 visit (up to day 252)

*** V11a and V11b apply to patients who did not respond at Week 16 and were re-allocated to BI655130 treatment

Repeated and unscheduled efficacy, safety and biomarker measurements will be handled similarly to scheduled measurements and will also be assigned to a time window depending upon the date of measurement.

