Only one observation per time window will be selected for statistical analysis at a particular visit – the value which is closest to the protocol planned visit day will be selected. If there are two observations which have the same difference in days to the planned day, the later value will be selected. If there are two observations on the same day, the worst value will be selected.

Assignment of efficacy observations to visits based on time windows will be based on the non-imputed (observed) data.

For visits without an assigned value based on time windows, a value will thereafter be imputed as defined in [Section 6.6](#). Imputation of efficacy endpoints, when applicable, will be performed based on all available observations obtained during the on-treatment period, irrespective of whether the observation was selected in any time window.

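### SAP Table 6.7: 2 gives conflicting analysis windows after Week 16: Day 252 overlaps V11a and V11b, the responder V10 end has no precedence rule, and one V11 visit feeds two analysis visits

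*SAP*

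**What the plan says.** SAP 6.7, Table 6.7: 2, sets the analysis windows after the Week 16 visit.

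- **V10** (planned Day 197, protocol window Days 194 to 200) starts at Day 183. Its end cell lists three limits separated by slashes: Day 210, last dose plus 16 weeks, and the EoS visit date.
- **V11a** starts at Day 211 and ends at Day 238, last dose plus 16 weeks, or the EoS visit date.
- **V11b** starts at Day 239 and ends at last dose plus 16 weeks or the EoS visit date.

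The footnote to V10 adds a limit for each group. For responders: "V10 EoS applies to patients who responded at Week 16 (up to LD+16 weeks". For non-responders: "Non-responders receive the last dose of the BI655130 at that Week 28 visit (up to day 252". The footnote to V11 reads: "V11a and V11b apply to patients who did not respond at Week 16 and were re-allocated to BI655130 treatment".

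Protocol Flow Chart footnote 18 gives non-responders a single V11. Those going to the extension trial, having reached EASI50, have it no earlier than Week 32. For the others: "Non Responder patients not participating in the extension trial will complete a V11/FU1 visit between Week 32-44". Their later contact is a safety phone call, for which the Flow Chart marks no EASI, SCORAD or IGA. SAP Section 5 instead places the non-responder end-of-study visit at Week 44.

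On empty windows SAP 6.7 says: "For visits without an assigned value based on time windows, a value will thereafter be imputed as defined in" Section 6.6. For binary endpoints, Section 6.6.2 imputes failure unless the visits on both sides are successes. Continuous endpoints are left to the MMRM.

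**The concern.** Each observation after Week 16 should have one place in the analysis, and two programmers should reach the same tables. Three features of Table 6.7: 2 prevent this.

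(a) A V10 window running to Day 252 shares days with both V11 windows.

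(b) Nothing says whether the earliest, the latest or a group-specific end applies to V10. Under the limit that the footnote names for responders, a compliant visit can be left without a window.

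(c) One scheduled V11 efficacy visit can fill only one of two analysis visits. For a binary endpoint the other would be completed by the non-response rule, although the patient missed nothing.

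At stake are the descriptive re-allocation summaries. Protocol 3.2 gives the duration of response off treatment as the reason for stopping treatment in responders, so their Week 28 result deserves an unambiguous window.

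**Working it through.** **Inputs.** V10 at Day 197, protocol window 194–200; V11a from Day 211 to Day 238; V11b from Day 239, planned Day 309 (SAP Table 6.7: 2). V6 at Day 85, window 82–88 (SAP Table 6.7: 1). V6 is the last blinded infusion, hence the last dose for responders (Protocol 6.2.2). Sixteen weeks is 112 days (SAP Table 6.1: 2). Visits are counted from Day 1 (Protocol 6.1), so V10 stays at Days 194–200 whatever the V6 date.

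**1. Reproducing the table's own limits.** The extended ends follow one rule: midpoint of adjacent planned days, minus 1. It gives 21, 42, 70, 98, 126, 154 and 182, all as printed; for example (169 + 197)/2 − 1 = 182.

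- Day 210: (197 + 225)/2 − 1 = 210, with Week 32 taken as 32 × 7 + 1 = Day 225.
- Day 252: (197 + 309)/2 − 1 = 252.

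Day 252 therefore fits a layout with a single V11 at Day 309, not the present one with V11a and V11b. That it is left over from such a layout is an inference from the arithmetic.

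**2. Overlap.** Days 211–238 are 28 days (all of V11a) and Days 239–252 are 14 days of V11b: 28 + 14 = 42. SAP 6.7 then keeps the value closest to the planned day. A V10 done on Days 194–200 is at most 3 days from Day 197. A V11 value from Day 211 onward is at least 211 − 197 = 14 days away, so V10 is kept. The overlap acts in two cases. If V10 is missing, a V11 value up to Day 252 can be taken as V10. If V10 is done after Day 210, its value fits two windows.

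**3. Responder V10 end.** With the last dose on day d, the footnote's limit closes V10 on day d + 112.

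| Last dose (V6) | V10 closes | On-schedule EoS days left outside |
|---|---|---|
| 82 | 194 | 195–200 (6) |
| 83 | 195 | 196–200 (5) |
| 84 | 196 | 197–200 (4) |
| 85 | 197 | 198–200 (3) |
| 86 | 198 | 199–200 (2) |
| 87 | 199 | 200 (1) |
| 88 | 200 | none (0) |

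The sum is 6 + 5 + 4 + 3 + 2 + 1 + 0 = 21 of 7 × 7 = 49 compliant date pairs, and the largest excess is 200 − 194 = 6 days. If Day 210 or the EoS visit date governs, the count is 0 of 49.

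**4. One V11, two analysis visits.** Take a non-responder whose V11 falls between Day 225 (Week 32) and Day 238. V11a is filled and V11b is empty. V11b has no later visit, so the two-neighbour exception cannot apply and a binary outcome is imputed as failure. This includes a patient who left for the extension having reached EASI50. If V11 falls from Day 239 on, V11a is empty and counts as success only if V10 and V11b both do. An unscheduled assessment could fill the empty window.

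**The case against.** The best defence is that little observed data would be misplaced. Much of that stands.

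- **Overlap.** A reader might infer that 42 days of V11 data are at risk. The closest-day rule does not allow that when an on-schedule V10 exists, and V10 is a dosing visit for non-responders. The Day 252 phrase also sits grammatically with the last dose. A window limit is the more natural reading, because it parallels the responder limit in the same footnote of a window table. Read as a dosing limit, it would still disagree with Day 197 ± 3.
- **Responder end.** A reader might turn 21 of 49 into an expected loss of 43% of responder visits. That needs uniform, independent visit offsets, which the documents do not give. Flow Chart footnote 18 ties the responder end-of-study visit to 16 weeks after last treatment, which would make offsets dependent. The loss also arises under only one of the three listed ends, and SAP Table 6.1: 1 runs the re-allocation phase through the EoS visit.
- **V11b.** A reader might infer that the EASI50 rate at V11b would fall by the whole share of patients who roll over. The visible text names EASI50, EASI75 and IGA response at Weeks 4 and 16 only. Other endpoint sections are blacked out, so whether such a V11b rate is produced cannot be seen. No roll-over rate is given, and a roll-over after Day 238 would fill V11b. SAP 6.6.2 also plans observed-data frequency tables, and SAP Section 7 lists all individual values.

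Keeping V11a and V11b apart also has a purpose: it separates about 4 from about 16 weeks since the last dose.

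The inconsistency itself remains. None of these points says which V10 end governs, or exempts an unscheduled V11 window from imputation.

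**Conclusion.** Table 6.7: 2 is internally inconsistent and should be repaired, but the consequences are small. (a) Day 252, read as a window limit, conflicts with the V10, V11a and V11b rows and acts only when V10 is missing or very late. (b) An on-schedule responder end-of-study visit can fall up to 6 days outside V10 if last dose plus 16 weeks governs, and cannot if Day 210 or the visit date governs; the SAP does not choose. (c) For any binary endpoint summarised at V11a and V11b, a patient seen once, by Day 238, is imputed as a failure at V11b. Continuous endpoints are not imputed.

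The documents do not support a claim that the trial's conclusions are at risk. SAP 6.1 makes the re-allocation results descriptive, and the Week 16 primary endpoint uses Table 6.7: 1 and is untouched. The size in (c) cannot be stated without a roll-over rate and sight of the blacked-out endpoints.

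**What to change.** Make three edits to SAP 6.7 and 6.6.2 before the final database lock.

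1. Reconcile Day 252 with the V10, V11a and V11b rows so that the analysis windows do not overlap. Word this as an analysis window only; it should not set or imply a dosing limit.
2. State that the responder V10 window runs to the EoS visit date. Do not add a cut at last dose plus 16 weeks or at Day 210. A Day 210 cut would leave a late responder visit with no window, since V11 is for non-responders only.
3. State that non-response imputation is not applied to whichever of V11a or V11b the patient was not scheduled to attend, including any window after a per-protocol exit to the extension. Either keep both windows with observed data only, or use one V11 analysis visit reported with weeks since last dose. The choice between these is a preference.

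The cost is minor SAP and programming edits. Keeping both windows gives smaller denominators at each; merging them mixes about 4 to 16 weeks since the last dose, which the added column would show.

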1- Initiation of randomized treatment at Visit 2 can only begin if the patient meets the criteria for Initiation of Treatment. Please refer to Sections [3.3.2](#) and [3.3.3](#).

2- At Visit 10, Non- Responders (NR) will receive their last study drug administration and Responders (R) will have their End of Study (EoS) visit.

3- Should a patient prematurely discontinue before their scheduled EoS every effort should be made to keep the patient in the trial and complete all of the remaining study visits or at a minimum an early EoS visit. Patients who prematurely discontinue before V7/Wk16 are considered Non-Responders.

4- C = Complete Physical Examination (PE) includes general appearance as well as evaluation of all organ systems; T = Targeted physical examination includes evaluation of organ systems associated with AE(s) symptoms or laboratory abnormalities. At Visit 10 complete physical examination will be performed for Responders (EOS), targeted physical examination will be performed for Non-Responders. Please refer to Section [5.2.1](#).

5- Vital signs will be assessed at predose, at approximately 5 minutes after the end of infusion, and 60 mins after the end of infusion at visits with i.v. administration.

6- Safety laboratory tests include clinical chemistry, haematology, coagulation, and urinalysis, and will be performed centrally. Local Labs may be used for dosing decisions prior to i.v. administration. Please refer to Section [5.2.3](#).

7- Only applicable for women of childbearing potential. S – serum pregnancy test (performed at screening). U – urine pregnancy tests will be performed at all other visits indicated in the [Flow chart](#). Urine pregnancy testing should be done prior to administration of study drug. Study drug should only be administered in case of a negative test result. (S) - in case of a positive urine pregnancy test, a serum pregnancy test will be done. Please refer to Section [5.2.5.2](#).

8- ECG measurements should always precede blood sampling and drug administration. Clinically significant abnormal findings should be reported as AEs in the eCRF.

9- Infection testing includes tuberculosis, hepatitis B, hepatitis C, and HIV assessments. Please refer to Table [5.2.3: 1](#). For the EoS visit only tuberculosis and hepatitis B testing will be performed. For Responders the Infection testing will be conducted at V10 (Week28) which corresponds to their EoS. For Non Responders the Infection testing will be conducted at V11.

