6.7 BASELINE, TIME WINDOWS AND CALCULATED VISITS

Measurements reported with date and time and taken prior to start of administration of trial treatment will be considered pre-treatment values. Measurements reported with a date only (and no time) and taken on the day of first administration of trial treatment will also be considered pre-treatment values. These pre-treatment values will be assigned to visits according to the nominal visit number as recorded on the eCRF or as provided by the laboratory. For definitions used in Safety analyses, refer to [Section 7.8](#).

Baseline, unless otherwise specified, is defined as the last measurement collected prior to the start of administration of the trial treatment.

Measurements taken after start of administration of trial treatment will be considered either on- or off-treatment values based on the definition in [Section 6.1](#), and will be assigned to visits for statistical analysis, if applicable, as defined below.

Analysis of AE data, concomitant medication or non-drug therapies will not be based on visits. Therefore, no assignment to time windows will be necessary for such data.

For derivation of the last value on treatment, minimum value on treatment, and maximum value in the trial phase, all values from the relevant phase (whether or not collected in any time window; see [Table 6.1: 1](#) for definition of the trial periods/phases) will be considered; these will be derived for analysis of laboratory and vital signs data. For identification of potentially clinically significant abnormal laboratory values, all values (whether or not selected in any time window) before the date of EoS Participation visit will be considered.

A graphical analysis of the ALT and total bilirubin will be performed (so called eDISH plot) based on the available data obtained during the on-treatment period.

All other safety, efficacy and biomarker measurements will be assigned to visits based on extended time windows around the planned visit dates, defined relative to the day of first trial treatment (which is scheduled for Visit V2). These extended time windows are defined in [Table 6.7: 1](#).

Table 6.7: 1 Time windows for assignment of efficacy, safety lab, vital signs, and biomarker measurements to visits for statistical analysis of the double-blind treatment period

Visit number / name	Visit label	Planned day	Time window (Days)				
			Window (per CTP)	Start (per CTP)	End (per CTP)	Start (extended)	End (extended)

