7.8.3 Vital signs

The analyses of vital signs (blood pressure, pulse rate, body temperature and body weight) will be descriptive in nature and will be performed for double-blind period and re-allocation period separately.

Descriptive statistics of vital signs over time and for the difference from baseline (see [Section 6.7](#)) will be provided by treatment, including summaries of the last value during the respective period (double-blind or re-allocation), the minimum value during respective period, and the maximum value during respective period (see [Table 6.1: 1](#) for definition of the trial periods/phases).

Clinically relevant findings in vital signs data will be reported as baseline conditions (at screening) or as AEs (during the trial) if judged clinically relevant by the investigator, and will be analysed as such.

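### The same-day worst-value rule in SAP 6.7 makes the by-visit change from baseline in vital signs not like-for-like at infusion visits (minor; descriptive tables only)

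*SAP*

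**What the plan says.** SAP 6.7 places vital signs in its visit-window scheme. The title of Table 6.7: 1 covers "assignment of efficacy, safety lab, vital signs, and biomarker measurements to visits for statistical analysis of the double-blind treatment period", and Table 6.7: 2 does the same for the time after Week 16. Within a window, "Only one observation per time window will be selected for statistical analysis at a particular visit", namely the one closest to the planned day. Two tie rules follow. The first is: "If there are two observations which have the same difference in days to the planned day, the later value will be selected". The second is: "If there are two observations on the same day, the worst value will be selected".

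The protocol's Flow Chart, footnote 5, sets the number of readings: "Vital signs will be assessed at predose, at approximately 5 minutes after the end of infusion, and 60 mins after the end of infusion" on infusion days. Sections 5.2.2 and 6.2.2.1 repeat this.

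Baseline is a single value (SAP 6.7): "Baseline, unless otherwise specified, is defined as the last measurement collected prior to the start of administration of the trial treatment".

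SAP 7.8.3 then plans "Descriptive statistics of vital signs over time and for the difference from baseline" by treatment, separately for the double-blind and re-allocation periods, together with the last, minimum and maximum value in each period.

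**The concern.** The same-day rule suits an unplanned repeat measurement. Applied to a planned series around an infusion, it does two unwanted things. It takes an extreme of three readings at some visits and a single reading at others, so a visit profile can rise and fall with the infusion schedule when nothing has happened to the patient. It also mixes pre- and post-infusion readings in one column, so the table cannot show whether a value reflects the patient's general state or the hour after the infusion.

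The rule is also ambiguous. The SAP gives no direction for worst, and blood pressure, pulse and temperature can each be abnormal in both directions. Same-day readings are equally distant from the planned day, so they also meet the later-value rule. Two programmers could produce different tables from the same text.

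This matters because protocol 2.1.1 names safety and tolerability as the main objective and says they can only be analysed descriptively. The descriptive tables are therefore the evidence.

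**Working it through.** The documents state no figure that depends on this rule, so there is nothing to reproduce. The check counts readings and then sizes the effect.

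**Readings entering the by-visit change**

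| Visit | Infusion | Scheduled readings | Change from baseline, as written |
|---|---|---|---|
| Week 2 (V3) | none | 1 | one minus one |
| Weeks 4, 8, 12 (V4 to V6), both arms | yes | 3 | worst of three minus one |
| Weeks 20, 24, 28 (V8 to V10), non-responders | yes | 3 | worst of three minus one |
| Weeks 20, 24, 28, responders | none | 1 | one minus one |
| V11, non-responders | none | 1 | one minus one |

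The infusion visits come from protocol 6.2.2 and Flow Chart footnotes 2 and 16. Two visits are left out. Week 16 has its own vital-signs footnote under Table 6.7: 2, whose wording is unclear. For Day 1, a footnote to Table 6.7: 1 keeps readings taken after the start of infusion out of the Day 1 value.

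**Size of the shift with no true effect**

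Model: a reading is the patient's level, plus a visit deviation (SD s_v), plus within-visit variation (SD s_w). The three readings are treated as exchangeable and normal.

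- Worst = highest: the expected change is s_w × E[max of 3] = s_w × 3/(2√π) = 0.846 × s_w. Simulation gave 0.847. The between-visit part cancels from the mean.
- Worst = lowest: the same size, with a minus sign.
- Worst = furthest from baseline: the mean shift is 0, but the spread grows. With assumed s_w = 5 and s_v = 8, the SD of change from single readings is √(2 × (25 + 64)) = 13.3. In simulation it rises to 16.4 under this reading of the rule.
- Later-value rule instead: the 60-minute reading is chosen. There is no extreme-value shift, but a post-infusion value is still set against a pre-infusion baseline.

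The documents give no within-visit SD. Over an assumed range, taking worst as highest:

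| Assumed s_w (mmHg) | Artificial mean change (mmHg) |
|---|---|
| 4 | 0.846 × 4 = 3.4 |
| 6 | 0.846 × 6 = 5.1 |
| 8 | 0.846 × 8 = 6.8 |

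**Between groups**

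At Weeks 4, 8 and 12 both arms have three readings, so the expected BI 655130 minus placebo artefact is 0.846 × s_w − 0.846 × s_w = 0.

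**After the fix**

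With the pre-dose reading at every infusion visit, the expected change with no true effect is 0 at every visit.

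**The case against.** The strongest reply is that the rule was never meant for planned series. It speaks of two observations, follows a paragraph on repeated and unscheduled measurements, and overlaps with the later-value rule. The Week 16 footnote shows that the authors did separate vital signs around dosing at one visit, and SAP 6.1 leaves technical details to an ADS Plan that is not among the documents. The intended programming may therefore be sensible. This stands as a reason for caution about what will be done, but not as an answer to the text. SAP 6.7 states no exception for the other infusion visits, and vital signs are named in its scope.

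A second reply is that nothing important is lost. This is largely right. SAP 6.7 derives the period minimum and maximum from all values, individual values are listed, and infusion reactions are captured as AESIs and as a user-defined AE concept. A reader might infer that the infusion-reaction signal disappears; the documents do not support that. What is missing is a planned summary of the readings by time point.

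A reader might also infer a spurious difference between open-label and untreated patients after Week 16, since the former have three readings and the latter one. It would arise only if the two groups were tabulated side by side. The SAP does not clearly plan that: the safety columns in 6.1 contain no untreated group, and SAF-OL (6.3) holds only patients dosed after re-allocation. SAP 7.8 muddies this by referring patients without open-label drug to SAF-OL. The groups are in any case formed by response, not by randomisation.

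**Conclusion.** The point holds, as a minor one. Read as written, SAP 6.7 makes the by-visit change from baseline in vital signs not like-for-like at Weeks 4, 8 and 12, and at Weeks 20, 24 and 28 for non-responders. It also leaves the direction of worst and the precedence of the two tie rules open.

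The mean shift is about +0.85 or −0.85 within-visit SD if worst means highest or lowest. If it means furthest from baseline, the spread is inflated and the mean is not shifted. The mmHg figures rest on assumed SDs and on exchangeable normal readings; neither their size nor their sign can be taken from the documents.

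It would be wrong to conclude that the randomised safety comparison is biased. Any shift appears equally in the concurrent placebo column. No safety hypothesis is tested, and EASI and the primary analysis are untouched.

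**What to change.** In SAP 6.7 and 7.8.3:

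1. State that the same-day rule does not apply to planned vital-sign time points at infusion visits.
2. Use the pre-dose reading for by-visit values and for change from baseline.
3. Summarise the 5- and 60-minute readings as change from the same visit's pre-dose value, by treatment.
4. For true same-day repeats, define worst for each parameter and say which tie rule takes precedence.
5. Leave the period minimum and maximum on all values, as now.

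While editing, reconcile the SAF-OL definition in 6.3 with the sentence in 7.8 on patients not receiving open-label drug, so that it is clear whether untreated responders appear in any vital-signs table.

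The cost is a few sentences, programming on the existing pre- and post-infusion time points, and one extra descriptive table. No data collection changes.
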